### **Outcome measures**

Subjects' pain was assessed using the validated 11-point NRS (0 = no pain, 10 = worst pain imaginable). Pain level was evaluated at multiple time-points; pre-anesthetic injection with stimulus (VAD ON/VAD OFF) at 0s and 5s; the timepoint of anesthetic injection at 15s (NRS) with stimulus (VAD ON/VAD OFF); and 5s post-infiltration with no stimulus present. Patients communicated their pain level verbally at the above timepoints.

Relative change in NRS was calculated with the below:

$$\text{Relative Change} = 100 * \frac{NRS_{Initial} - NRS_{Final}}{NRS_{Initial}}$$

From the findings of Olsen et al., MCID and SCID was defined as a relative change of 22-56% and  $\geq 57\%$ , respectively.

## **Eligibility Criteria**

What is the age range of the subject population?

18 and older, all patients presenting for Mohs or Excisional Surgery with [name] at UPMC  
Dermatologic Surgery  
Enrolling Pitt medical students

What is their gender?

\* Both males and females

Provide a justification if single gender selected:

Will any racial or ethnic subgroups be explicitly excluded from participation?

\* No

For studies conducted in the U.S., do you expect that all subjects will be able to comprehend English?

\* Yes

## **Statistical Considerations**

Unpaired 2-tailed Student's t-test was used for univariate analysis of all variables for comparison of NRS means. A threshold for significance was set at  $p < 0.05$ . All values collected were analyzed to report mean values  $\pm$  standard error from the mean.

Multivariate linear regression analysis was used to compare categorical variables (age, sex, and treatment site). Multivariate analysis of the overall cohort identified  $p < 0.2$  for age, sex, and treatment site. All further subgroup analysis was performed using multivariate analysis with a threshold for significance set at  $p < 0.05$ . All statistical analyses were calculated by RK with Igor Pro (Wavemetrics, version 8) and STATA (StataCorp, version 13) software and confirmed with a consulting statistician ([name]).

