## Study Objectives

Determine how patients in an out-patient surgical setting interpret non-noxious stimulation, specifically focusing on vibration.

Perception of cutaneous stimuli is critical in the diagnosis and treatment of many dermatological diseases. However, there is little understanding of how global sensations varies across populations.

Specific aim 1: Variable perception and interpretation of a non-noxious stimulus.

Hypothesis: Different patient populations will show subtle, if any, difference of non-noxious stimulation.

Rationale: Historically, there is evidence citing differences in perception of acute noxious stimuli across age, history of exposure to pain, and gender. Little information is available regarding non-noxious stimuli. In previous work from our group and validated by other researchers, patients are largely able to tolerate the non-noxious stimulation of vibration. Our aim here is to determine whether this tolerability and interpretation shows any difference across cohorts, specifically those in an outpatient surgical setting.

Specific aim 2: Variable perception and interpretation of a noxious stimulus following a non-noxious stimulus

Hypothesis: Different populations will show a significant difference in perception of noxious stimulation

Rationale: As previously cited, different cohorts of humans has a wide variety in how pain, both acute and chronic, is perceived. In this aim, we can identify how the noxious stimulus of an injection of anesthetic varies across populations in an out-patient surgical setting. Further, it is known that the application of vibration prior to needle injection significantly reduces the pain felt by the patient. This aim can determine how this change varies across different patient cohorts.

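### Subgroup tests at an unadjusted 0.05 do not answer Aim 2; one arm-by-factor interaction per factor, Holm-adjusted or labelled exploratory, would

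*Combined protocol and SAP*

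**What the plan says.** The Statistical Considerations section describes the following steps.

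- Univariate comparisons: "Unpaired 2-tailed Student's t-test was used for univariate analysis of all variables for comparison of NRS means", with significance at p<0.05.
- A regression: "Multivariate linear regression analysis was used to compare categorical variables (age, sex, and treatment site").
- Its result: "Multivariate analysis of the overall cohort identified" p<0.2 for age, sex and treatment site.
- What follows: "All further subgroup analysis was performed using multivariate analysis with a threshold for significance set at" p<0.05.

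The section does not say what the 0.2 threshold was for, which coefficients it refers to, how many subgroup tests were run, or whether arm was a term in the regression. It states no multiplicity adjustment and no arm-by-factor interaction.

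Under Study Objectives, both specific aims concern differences between groups of patients. The hypothesis for Aim 2 is that populations differ in how they perceive a noxious stimulus. Its rationale ends by asking how the reduction in injection pain from prior vibration differs between patient groups.

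**The concern.** Two things do not fit together.

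The closing question of Aim 2 is whether the vibration effect (ON against OFF) is larger in some patients than in others. That is a comparison of effects between subgroups. The plan offers subgroup tests, each at 0.05. Two subgroups with the same true benefit can fall on opposite sides of 0.05 because of size or chance, and a reader would then see a difference that was never tested.

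Differences between patient groups are also a main product of this study, and every test of them stands at an unadjusted 0.05. With several factors, several levels and several pain readings, some nominally significant subgroup results are to be expected even if nothing differs.

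The p<0.2 step adds uncertainty. Significance is already set at 0.05 in the same section, so 0.2 looks like a rule for carrying factors forward. If so, factors were chosen on the data used to test them, and possibly on a quantity (the main effect on pain) other than the one Aim 2 asks about.

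**Working it through.** The documents give no sample size, SD, effect size, power or family-wise error level, so there is no design figure to reproduce.

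**Inputs from the documents.** Three factors, an overall-cohort threshold of 0.2 and a subgroup threshold of 0.05 (Statistical Considerations); randomized parallel arms, ratio not stated (Study design); four NRS readings, none named as primary (Outcome measures: "Pain level was evaluated at multiple time-points; pre-anesthetic injection with stimulus (VAD ON/VAD OFF) at 0s and 5s", then at injection and after infiltration).

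**Assumptions.** Two levels per factor. For the simulations: 1:1 arms, three binary factors, normal outcome with SD 1, N = 60, 100 or 200, and 4,000 runs per setting.

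**Step 1: which test fits the question.** Let d1 and d0 be the ON-minus-OFF difference in the two levels of a factor.

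- Aim 2's closing question is whether d1 - d0 = 0.
- A subgroup test asks whether d1 = 0, or whether d0 = 0.
- A main-effect coefficient asks whether average pain differs between the levels.

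Only an arm-by-factor term estimates d1 - d0, and none is specified.

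**Step 2: error over several tests.** For k independent tests at 0.05 with no true effects, P(at least one p<0.05) = 1 - 0.95^k.

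- k = 3 (one test per factor): 1 - 0.857 = 14.3%. Simulated for three interactions: 14.7%, 13.9% and 14.2% at N = 60, 100 and 200.
- k = 6 (two levels of each factor): 1 - 0.735 = 26.5% if independent. The six subgroups share patients. Simulated with that overlap: 21.2%, 22.1% and 21.8%.
- k = 12 (three factors by four readings): 1 - 0.540 = 46.0% if independent. Readings from one patient are likely to be correlated, so this is an illustration and not an estimate.

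**Step 3: what the p<0.2 step does under each possible reading.**

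- *The same main effect is screened at 0.2 and then re-judged at 0.05 on the same data.* A null factor that passed reaches p<0.05 with probability 0.05/0.20 = 25% (simulated 24-26%). The p-value is inflated, under this reading only.
- *Main effects are screened, then interactions are tested.* Error per test among null factors that passed is 5.6%, 4.4% and 4.7%, so the screen itself causes no inflation.
- *The step only justified keeping three adjustment covariates.* There is no selection effect on the subgroup tests, and step 2 applies unchanged.

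**Step 4: after the change.** Holm across three interactions compares the ordered p-values with 0.05/3 = 0.0167, 0.05/2 = 0.025 and 0.05. This holds the family at 5% or less.

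**The case against.** The plan never says that p<0.2 decided entry or that it refers to main effects. It can fairly be read as a reason for keeping three covariates. That stands, so the criticism of the screen must stay conditional.

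A genuine screen can also reduce testing. Under the null, simulated within-subgroup error over the factors that passed was only about 6%, because few null factors get through. Here all three named factors are reported as meeting 0.2, so nothing is shown to have been saved.

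The study calls itself descriptive, and Aim 2's hypothesis sentence, taken alone, is about differences in pain between populations, which a main-effects regression can address. This supports offering an exploratory label as an alternative to adjustment. It does not settle the closing question about the vibration effect.

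Three stronger conclusions might be inferred and are not supported.

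- *Real effect modifiers were screened out.* All three named factors met the threshold, and no factor is said to have been dropped. Whether a main-effect screen would lose a modifier depends on the OFF arm. With assumed n = 80, SD 2 and a vibration effect of -2.5 points in one level and 0 in the other, the factor passes about 92% of the time if OFF-arm pain is equal in the two levels. It passes about 18% of the time only if OFF-arm pain differs by an exactly offsetting 1.25 points.
- *Pain history was a planned factor that disappeared.* The sentence "there is evidence citing differences in perception of acute noxious stimuli across age, history of exposure to pain, and gender" is background in the rationale for Aim 1, not a list of analysis factors.
- *The screen inflates the interaction tests.* Step 3 shows that it does not. The inflation there comes from the number of unadjusted tests.

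**Conclusion.** The point holds in a limited form. The plan tests subgroups at 0.05 without multiplicity control and specifies no arm-by-factor interaction, although one of its aims asks how the vibration effect varies between patients. The chance of at least one false subgroup finding is about 14% for 3 tests and 21-26% for 6. The lower end for 6 allows for overlapping subgroups and the upper end assumes independence. The number of tests and of levels per factor is assumed throughout, because the plan gives neither.

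The p<0.2 step is unclear rather than shown to be wrong. If it chose the factors, it was a data-driven basis for picking effect modifiers, and main effects re-judged at 0.05 would carry inflated p-values. If it did not, its role still needs stating. The overall ON-against-OFF comparison is not affected by this point. It is a cheap improvement to the subgroup analysis.

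**What to change.** 1. State what the p<0.2 step was for, and do not use it to choose subgroup factors.
2. Keep age, sex and treatment site in the model whatever their p-values, together with arm.
3. For Aim 2, test one arm-by-factor interaction per factor, using a joint test where a factor has more than two levels. Report the estimated difference in vibration effect with its confidence interval.
4. Either apply Holm across the three interactions or label all subgroup results exploratory.

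The cost is a change of wording and a re-run of one regression on data already collected. The downside is that fewer subgroup results will be called significant. Interaction tests can also have limited power. In the simulation, with an assumed modifier of 0.8 SD, power at an unadjusted 0.05 was about 30%, 48% and 79% at N = 60, 100 and 200, and Holm would lower it. A non-significant interaction should therefore not be reported as evidence that vibration works equally well in all patients.

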### **Study design**

A randomized, partially-blinded, parallel-group clinical study of perception and interpretation of a non-noxious vibration stimulus compared to placebo (vibratory device in “off” mode) during syringe-mediated local cutaneous infiltration of anesthetic was performed. The protocol was approved by the University of Pittsburgh Institutional Review Board (PRO17110134) and conforms to the ethical guidelines of the Declaration of Helsinki.

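### Aim 2 promises to show how the vibration effect varies across cohorts, but the plan specifies no arm-by-factor interaction, no other between-subgroup comparison and no multiplicity rule

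*Combined protocol and SAP*

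**What the plan says.** Specific aim 2, under Study Objectives, has two parts.

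- Its hypothesis concerns pain perception as such: "Different populations will show a significant difference in perception of noxious stimulation".
- Its rationale goes further. It states that "it is known that the application of vibration prior to needle injection significantly reduces the pain felt by the patient" and then adds: "This aim can determine how this change varies across different patient cohorts". The change in question is the reduction in injection pain from vibration.

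The Study design section describes "A randomized, partially-blinded, parallel-group clinical study of perception and interpretation of a non-noxious vibration stimulus compared to placebo", the placebo being the same device switched off. The vibration effect is therefore a contrast between randomised arms. Outcome measures lists four NRS assessments, one of them "the timepoint of anesthetic injection at 15s (NRS) with stimulus (VAD ON/VAD OFF"), and names none as primary.

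Statistical Considerations is the only statistical section. It provides:

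- a two-tailed unpaired test: "Student's t-test was used for univariate analysis of all variables for comparison of NRS means", at p < 0.05;
- a linear regression on three factors (the text reads "Multivariate linear regression analysis was used to compare categorical variables (age, sex, and treatment site");
- a report that these three factors reached p < 0.2 in the overall cohort;
- the subgroup rule: "All further subgroup analysis was performed using multivariate analysis with a threshold for significance set at" p < 0.05.

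The regression outcome, any arm term and the terms of the subgroup models are not stated.

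**The concern.** The stated regression can address the hypothesis of Aim 2, because whether age, sex or site groups report different pain is a question about factor main effects. It does not, as described, address the second part. To show that vibration works better in one cohort than in another, the ON-OFF difference must be compared between cohorts, and nothing in the plan does that.

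The only cohort-specific decision rule in the plan is a subgroup p-value against 0.05. A significant result in one subgroup and a non-significant result in its complement is not evidence that the two effects differ; it often reflects only the loss of power when the sample is split. A reader who uses the subgroup p-values in that way can report effect variation where there is none. With three factors and no multiplicity rule, there are several chances to do so.

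**Working it through.** **No figure to reproduce.** The documents give no sample size, SD, power, effect size or allocation ratio. Their only numerical inputs here are the two-sided 0.05 threshold, the p < 0.2 result, the three factors and the four time points. Everything else below is assumed.

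**Step 1. One factor, identical true effects.** Let P be the power of the overall ON-OFF comparison, with noncentrality d = 1.96 + z(P), or d = 0 if there is no effect. In a subgroup holding a share f of the patients:

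- power p = Pr(|Z + d√f| > 1.96);
- the two subgroups disagree on significance with probability p₁(1 − p₂) + p₂(1 − p₁).

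Example at P = 80% with equal halves: d = 1.96 + 0.84 = 2.80; d√0.5 = 1.98; p = 0.508 in each half; discordance = 2 × 0.508 × 0.492 = 0.50.

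| Overall power | d | Discordance, 50:50 | Discordance, 70:30 |
|---|---|---|---|
| 50% | 1.96 | 41% | 42% |
| 80% | 2.80 | 50% | 55% |
| 90% | 3.24 | 47% | 54% |
| 99% | 4.29 | 24% | 36% |
| 99.9% | 5.05 | 10% | 22% |
| No effect | 0 | 10% | 10% |

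The true effect is the same in both subgroups in every row. A test of the interaction rejects wrongly in 5% of trials in every row.

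**Step 2. Three factors.** Simulation with three independent 50:50 binary factors, a normal outcome with SD 1, a uniform effect and 2,500 replicates (Monte Carlo standard error at most 1 percentage point). The entries are the share of trials in which at least one factor shows one significant and one non-significant subgroup t-test.

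| Uniform effect | 25 per arm | 50 per arm |
|---|---|---|
| 0 SD | 22% | 20% |
| 0.5 SD | 59% | 74% |
| 1.0 SD | 72% | 26% |
| 1.5 SD | 25% | 0.6% |

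In the same simulated data, three unadjusted interaction tests gave at least one false difference in 13–15% of trials (independent tests would give 1 − 0.95³ = 14.3%). Holm adjustment brought this to about 5%.

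**Step 3. Power of the correct test.** With equal halves, each subgroup effect has twice the variance of the overall effect, so their difference has four times that variance and twice the standard error. For an interaction as large as the overall effect, the noncentrality is therefore d/2.

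- Overall power 80%: d/2 = 1.40. Power is 29% at 0.05 and 16% at the first Holm step (0.05/3 = 0.0167, critical value 2.39).
- Overall power 90%: d/2 = 1.62. Power is 37% and 22% respectively.

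**The case against.** There is a fair case for giving this less weight.

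- **The claim is in a rationale, not a hypothesis.** The stated hypothesis of Aim 2 can be addressed by the regression. This stands, and it confines the gap to the effect-variation claim.
- **The study calls itself descriptive.** A multiplicity rule matters less in a descriptive study. But the plan applies p < 0.05 to its subgroup analyses and says the aim can determine variation, so the label softens the point without removing it.
- **The unspecified subgroup model might have contained an interaction.** It might. The criticism is that none is specified, not that none was fitted.
- **The error rates assume a misreading that the plan does not describe.** That is correct. The simulation also uses subgroup t-tests, whereas the plan says subgroups were analysed by multivariate methods. The results run from 0.6% to 74% depending on assumed inputs. They illustrate a principle and do not estimate this trial's error rate.
- **The plan is written in the past tense and already reports a result.** New wording cannot now serve as prespecification. The gain is limited to how subgroup claims are analysed and reported.

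None of this supplies a test of whether the vibration effect varies.

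**Conclusion.** The concern holds. The plan specifies no interaction test, no other between-subgroup comparison of the ON-OFF effect and no multiplicity rule, so the effect-variation part of Aim 2 has no valid test. The randomised ON-OFF comparison and the main-effect hypothesis of Aim 2 are not affected. This should be fixed, but it does not undermine the trial as a whole.

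If discordant subgroup p-values are read as differences, a single evenly split factor would mislead in about 10% to 50% of trials across the scenarios examined, against 5% for an interaction test. Those figures rest on assumed power, subgroup shares and normality. The omission itself rests on the text alone.

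**What to change.** State the model. On all randomised participants, regress NRS at injection (15 s) on arm, age, sex, treatment site, arm-by-age, arm-by-sex and arm-by-site, with a joint test for any factor with more than two levels. Base any claim that the effect differs on the interaction tests, Holm-adjusted across the three factors. Report the ON-OFF difference in each subgroup with a 95% confidence interval, as description only. Do not use the p < 0.2 result to justify subgroup claims. Label the analyses exploratory, and post hoc if they are added after the data were seen. If no significance claims are to be made, interaction estimates with confidence intervals under an explicit exploratory label would be the minimum adequate change.

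The cost is some SAP wording and one regression on data already collected. Two limits should be stated. First, interaction power is low (29% and 16% in the 80% case above) and would be lower still for uneven splits; arm-by-site cells may be sparse if there are many site categories, a number the documents do not give. Second, few subgroup claims are likely to be supported, and a non-significant interaction does not show that the effect is uniform.
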